4.5.2 Prohibited Medications/Treatments

The decision to administer a prohibited medication/treatment is taken with the safety of the study participant as the primary consideration. When possible, Allergan should be notified before the prohibited medication/treatment is administered.

During the study, patients must not participate in other investigational drug or device studies.

Nonstudy IOP-lowering Treatments

Any concurrent nonstudy IOP-lowering treatment (eg, topical ophthalmic medication containing an ocular antihypertensive, LT) is prohibited in either eye during the study (through Week 52), unless necessary for the safety of the patient due to inadequate control of IOP as determined by the investigator. Inadequate control of IOP should be confirmed at a subsequent visit (scheduled or unscheduled visit). Initiation of treatment in one eye should not automatically lead to initiation of treatment in the contralateral eye. Each eye should be evaluated on an individual basis when determining the need for additional nonstudy IOP-lowering treatments. If nonstudy IOP-lowering treatment is initiated, the investigator will be expected to attest to the need for additional nonstudy IOP-lowering treatment for safety reasons for each eye individually. Use of any concurrent nonstudy IOP-lowering treatment with any known effect on study outcomes (eg, crossover effect on the contralateral eye) is prohibited during the study.

In order to maintain patient masking to treatments assigned to each eye, patients who have received nonstudy topical IOP-lowering treatment in a Bimatoprost SR eye will receive Sham Bimatoprost SR administration in that eye on the Bimatoprost SR Cycle 2 (and Cycle 3 for Stage 1 patients) administration day(s). If nonstudy topical IOP-lowering medication is initiated in an SLT eye, the patient will continue to receive Sham Bimatoprost SR administration in the SLT eye on the administration day(s). In all cases, the contralateral eye that does not require nonstudy topical IOP-lowering medication will maintain the same

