7.1 Analysis Populations

The intent-to-treat (ITT) population is defined as all randomized patients, and will be used for efficacy analyses.

The modified intent-to-treat (mITT) population is defined based on ITT population, but will exclude patients who did not receive the second implant after the implementation of Amendment 3. The mITT population will be used for the primary analysis.

The per-protocol (PP) population is defined as all patients in the ITT population who have no protocol deviations affecting the data for primary efficacy analysis for all visits (Week 4, Week 12, and Week 24) in both eyes. A list of patients excluded from the PP population will be finalized prior to database lock.

The safety population is defined as all patients who received treatment and will be used for safety analyses.

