### **6.1 INTENT-TO-TREAT POPULATION**

Patients whose primary eyes were randomized to receive either Bim SR or SLT treatment will be referred to as randomized patients. The intent-to-treat (ITT) population is defined as all randomized patients, and will be referred to as “ITT population” in this SAP and

TFLs. Analyses using the ITT population will be based on the randomized treatment assigned to each eye.

The modified intent-to-treat (mITT) population is defined based on ITT population, but will exclude patients who could not receive the second implant due to the discontinuation for the Bim SR 15µg dose strength implemented in [protocol Amendment 3](#). The exclusion algorithm is as follows:

- If a patient had a missing Cycle 2 Day 1 Bim SR administration date with study exit date after March 19, 2020 (IWRS deactivation date), unless the patient had AE leading to drug withdrawn or received a rescue medication before March 19, 2020 in planned Bim SR eye, then the patients will be excluded from the mITT.

The reason for a missing Cycle 2 Day 1 Bim SR administration date is only due to the discontinuation for the Bim SR 15µg dose strength in protocol Amendment 3, not due to AE leading to drug withdrawn or rescue medications.

The mITT population will be used for the primary analysis.

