#### **10.1 PRIMARY EFFICACY ANALYSIS**

The primary efficacy variable is Hour 0 IOP change from baseline (follow-up value minus baseline value, thus negative values reflect IOP reduction from baseline) assessed at Weeks 4, 12, and 24. Intraocular pressure values at Hour 0 at Baseline visit is considered as the baseline values.

Baseline and Weeks 4, 12 and 24 Hour 0 IOP measurements with their changes from baseline will be descriptively summarized.

Primary efficacy analysis will be performed for patients in the mITT population. The null and alternative hypotheses for the comparison between Bim SR treated eyes and SLT treated eyes at Weeks 4, 12, and 24 are:

- Null hypothesis: the difference in mean IOP change from baseline between the Bim SR and SLT eye (Bim SR minus SLT) is  $> 1.5$  mmHg.
- Alternative hypothesis: the difference in mean IOP change from baseline between the Bim SR eye and SLT eye (Bim SR minus SLT) is  $\leq 1.5$  mmHg.

Hour 0 IOP change from baseline will be analyzed using a mixed effect model for repeated measurement (MMRM). The model will include Hour 0 IOP change from baseline as the response variable and treatment, visit, eye, baseline Hour 0 IOP, treatment-by-visit, treatment-by-baseline Hour 0 IOP, treatment-by-eye, visit-by-eye interactions as covariates. Unstructured covariance matrix for study visit and compound symmetry correlation for eyes will be used for repeated measures on the same patient. If the model fails to converge, alternative covariance structures may be used in the MMRM analysis. If the model fails to converge with alternative covariance structures, multiple imputation (MI) will be implemented before MMRM.

The mean difference in the Hour 0 IOP change from baseline between the Bim SR eyes and SLT eyes (Bim SR minus SLT) in the mITT population and the corresponding 95% confidence intervals (CI) will be constructed at each visit from MMRM analysis. The noninferiority comparison for Bim SR versus SLT at Weeks 4, 12, and 24 is the primary analysis. If the upper limit of the 95% CI is  $\leq 1.5$  mmHg at all 3 visits, Bim SR 15  $\mu$ g statistical noninferiority to SLT is considered demonstrated.

For additional clinical consideration, Bim SR is considered clinically noninferior to SLT if the upper limit of the 95% CI is  $\leq 1.0$  mmHg at 2 out of the 3 visits of Weeks 4, 12, and 24.

Sample SAS® code for primary analysis is shown as below:

```
proc mixed data=iop4;
  where avisitn >1;

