## **16.0 DATA HANDLING CONVENTIONS**

### **16.1 EFFICACY DATA**

As stated in protocol [Section 5.9.1.5](#) Retreatment with Bim SR, when eye(s) received non-study IOP lowering medication or procedure, to avoid confounding of efficacy data, IOP measurements obtained after initiating the use of non-study IOP-lowering medication or procedure in an eye will be treated as missing for that eye.

Additionally, handling of missing data will be supplemented by sensitivity analyses using multiple imputation and tipping point (adding different penalties on the imputed values) approach.

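### The SAP's mITT rule has no Week 16 due-date condition, so among patients not yet due on 19 March 2020 and followed beyond it, membership of the primary set depends on what happened in the Bim SR eye

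*SAP*

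**What the plan says.** Protocol 7.1 defines the mITT as the ITT population but says that it "will exclude patients who did not receive the second implant after the implementation of Amendment 3". It states no exception.

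SAP 6.1 turns this into an algorithm. The exclusion condition reads: "If a patient had a missing Cycle 2 Day 1 Bim SR administration date with study exit date after March 19, 2020 (IWRS deactivation date". The exception follows: "unless the patient had AE leading to drug withdrawn or received a rescue medication before March 19, 2020 in planned Bim SR eye". The wording leaves open whether the date and the eye qualify the adverse-event limb as well as the rescue limb. The SAP then gives the intent: the second implant should be missing only because the 15 µg dose was discontinued, "not due to AE leading to drug withdrawn or rescue medications".

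The set carries the main result. SAP 10.1 states: "Primary efficacy analysis will be performed for patients in the mITT population". The superiority test (SAP 10.2) and the alternative-covariance MMRM (SAP 10.4) use it too.

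Two other provisions decide what a retained patient contributes. Nonstudy IOP-lowering treatment is prohibited "unless necessary for the safety of the patient due to inadequate control of IOP as determined by the investigator" (Protocol 4.5.2), so rescue is related to the outcome. Under SAP 16.1, "IOP measurements obtained after initiating the use of non-study IOP-lowering medication or procedure in an eye will be treated as missing for that eye".

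**The concern.** Take two patients due for Week 16 in May 2020, both followed past 19 March. Neither could receive a second implant. One had the Bim SR eye rescued in February and is kept. The other had a controlled Bim SR eye and is dropped, even if the SLT eye was rescued. In this group, entry to the primary set depends on a post-randomisation event in one treatment, with no counterpart for the other.

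A retained patient with a rescue after a primary visit brings Bim SR-eye readings that are high because they led to rescue, set against an SLT eye that was not selected in that way. The comparable late patients with a good Bim SR result are absent. The paired difference moves upward at the visits before rescue and, through the model, at later ones. At stake is some power for noninferiority and superiority, and a primary set that is hard to describe as free of outcome-based selection.

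**Working it through.** **1. The plan's own power figures (SAP 14.0).** Inputs: SD 4 mm Hg, between-eye and within-patient correlations 0.5, true difference 0, two-sided 0.05, 144 patients.

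- SD of the paired difference = 4 × √(2 × (1 − 0.5)) = 4; SE = 4/√144 = 0.333.
- Power per visit = Φ(margin/SE − 1.96): 99.4% at 1.5 mm Hg and 85.1% at 1.0 mm Hg.
- With correlation 0.5 between visits: 98.5% for 3 of 3 at 1.5 (plan: about 98%) and 89% for at least 2 of 3 at 1.0 (plan: 90%).
- 144/0.9 = 160 enrolled. The plan's figures reproduce.

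**2. Size of the shift.** Let L be the number of late patients (Week 16 after 19 March 2020, exit after that date), p the share kept by the exception, d their mean excess paired difference, and 160 − L the remaining patients. None of L, p or d is in the documents; all are assumed.

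Shift = L·p·d / (160 − L + L·p)

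| L | p | d (mm Hg) | Kept (L·p) | Shift (mm Hg) |
|---|---|---|---|---|
| 10 | 2% | 3 | 0.2 | 0.6/150.2 = 0.004 |
| 25 | 6% | 4 | 1.5 | 6/136.5 = 0.04 |
| 40 | 10% | 5 | 4 | 20/124 = 0.16 |

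**3. Effect on power.** Here the same shift s is applied at all three visits: power per visit = Φ((margin − s)/SE − 1.96). The sample is held at 144 to isolate the exception from the loss of patients.

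| Shift (mm Hg) | 1.5 mm Hg, 3 of 3 (primary) | 1.0 mm Hg, at least 2 of 3 (additional) |
|---|---|---|
| 0 | 98.5% | 89% |
| 0.05 | 97.8% | 85% |
| 0.10 | 96.7% | 81% |
| 0.15 | 95.3% | 76% |

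**4. Check with a rescue mechanism.** Paired eyes were simulated with the plan's SD and correlations and no true difference. An eye was rescued when its IOP change exceeded a threshold, and its later values were missing. Visit means were fitted by generalised least squares as a stand-in for the MMRM. With 12% to 37% rescued by Week 15 (assumed), the kept late patients add +0.01 to +0.05 mm Hg for 10 to 20 late patients and +0.03 to +0.12 for 40. At 40 late patients and about 23% rescued, the shifts at Weeks 4, 12 and 24 are +0.09, +0.06 and +0.05. Power then falls from 98.5% to 97.5% (1.5 rule) and from 88.9% to 84.0% (1.0 rule). Without the late failures, the bias is about 0 (−0.01 to +0.01).

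**5. By route, for 4 patients kept per 120 others.**

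- Rescue after Week 4: +0.06 to +0.12 mm Hg.
- Rescue after Week 12: +0.03 to +0.11.
- Rescue before Week 4: −0.03, because no Bim SR reading at a primary visit remains.
- Withdrawal for an adverse event unrelated to IOP: about 0.

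**The case against.** The exception has a purpose. Under Protocol 4.5.2 a rescued Bim SR eye receives sham at Cycle 2, so Amendment 3 did not cost that eye its implant. The absence of an SLT counterpart follows from the same logic: rescue in the SLT eye leaves the Bim SR eye on its assigned regimen, so that patient did lose the implant to Amendment 3. For patients already past Week 16 by 19 March 2020, the clause also prevents Bim SR failures from being dropped. All of this stands. It explains the clause but does not make it outcome-free among patients who were not yet due.

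The effect is also limited. The ITT by-visit ANCOVA (SAP 10.4) lies outside the rule, and the PP population is drawn from the ITT. These let a reader look for a selection effect, but they are sensitivity analyses and do not change the primary set.

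A reader might infer that a late patient enters the primary set only if the Bim SR eye failed. The documents do not support that: anyone who exited on or before 19 March 2020 stays regardless, and withdrawal for an adverse event is not an IOP failure. A reader might also infer that the rule tilts the trial towards declaring noninferiority. The main direction is the opposite.

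**Conclusion.** The point holds in a limited form. For patients not yet due for the second implant on 19 March 2020 who exited later, membership of the primary set depends on a post-randomisation event in one treatment. The protocol definition and the SAP algorithm also differ.

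The size is unknown, because the documents give neither the number of such patients nor the rescue rate. The upper figure of 0.16 mm Hg needs every assumed input at its extreme. The power table assumes one constant shift at all visits, whereas in practice only pre-rescue readings and model borrowing carry the effect. On the primary 1.5 mm Hg rule the loss is about 1 to 3 percentage points for shifts of 0.05 to 0.15; the additional 1.0 mm Hg rule is more sensitive. The direction is mainly conservative. It would be too strong to say that noninferiority is likely to be missed for this reason. The change is still worth making, because an outcome-free rule is available at little cost.

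**What to change.** Replace the whole SAP 6.1 algorithm with a date rule. Compute each patient's Week 16 due date from the Cycle 1 administration date; SAP Table 16-1 already sets a Week 16 target (day 109) relative to the first implant, with a convention for patients who never received it. Exclude every patient whose due date falls after 19 March 2020 and keep every patient whose due date falls on or before it, whatever happened in either eye.

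Do not simply delete the exception. That would drop Bim SR failures among patients already past Week 16 and bias the comparison in favour of Bim SR.

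State in advance how boundary cases are handled. With the −2/+4 day window in Protocol Table 4, due dates from 15 to 21 March 2020 have a window that contains 19 March (due date − 2 ≤ 19 ≤ due date + 4). Reconcile the result with Protocol 7.1, and report how many patients the present exception would have kept.

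The cost is SAP wording and one reprogrammed flag. A few late patients leave the primary set (0 to 4 under the assumptions of step 2), and a few at the boundary may be classified differently from a strict reading of who could not receive the second implant.

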## 6.2 PER-PROTOCOL POPULATION

The per-protocol (PP) population is defined as all patients in ITT population who have no protocol deviations affecting the data for the primary efficacy analysis for all visits (Week 4, Week 12, and Week 24) in both eyes, and will be referred to as the “PP population” in this SAP and TFLs.

Since the primary eye and contralateral eye of a patient will contribute data separately for the two different treatments in the study, the data from one eye can be excluded from PP analysis due to a protocol deviation, but the patient can still be included in PP population because of valid data from the other eye.

Examples of protocol deviations that will result in removal of data from PP analysis include but are not limited to the following cases:

- For eyes with no study treatment, post-baseline data will be excluded from PP analysis, and
- For eyes that received both study treatments, data after the wrong treatment will be excluded from PP analysis.

A separate document will be prepared to describe data exclusion algorithm for PP analysis. All patients with data excluded from the PP analysis will be identified and

finalized prior to each database lock and will be displayed in a data listing with reason(s) for exclusion.

### **6.3 SAFETY POPULATION**

The safety population is defined as all patients who had received at least one treatment regardless of whether it was the planned treatment or not, and will be used for the safety analyses. Both eyes in the safety population are included in the ocular safety analyses. Ocular safety assessments will be based on the treatment received in each eye at the first administration. However, one patient received both SLT and Bim SR in the same eye. Safety assessment for the patient will be summarized under the Bim SR treatment group.

### **6.4 DATA COLLECTED BUT NOT ANALYZED**

Clinical lab test data, vital signs, pregnancy test, national eye institute visual functioning questionnaire, and general (non-ophthalmic) physical examination are collected only at Screening and will not be analyzed. Other data collected but not analyzed, will be described in the clinical study report.

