6.3.1.3 Vital Signs

The below vital signs will be measured at all patient visits and should be recorded prior to any invasive procedures.

- Pulse rate (beats per minute [bpm]): the patient should be resting in a seated position for a minimum of 5 minutes prior to measurement. Pulse rate is then counted over 30 seconds (and multiplied by 2 to obtain bpm).

Approval Date: 27-Mar-2020

- Blood pressure (mm Hg): the patient should be resting in a seated position for a minimum of 5 minutes prior to measurement. Systolic/diastolic blood pressure will be measured with a sphygmomanometer (manual sphygmomanometer or automated blood pressure measuring device).
- Temperature (°C/°F): the patient should be seated and the body temperature taken orally (or with an infrared forehead thermometer).

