7.3.4 Safety Analyses

Safety analyses will be performed for patients in Stage 1 and in Stage 2 safety populations. The Medical Dictionary for Regulatory Activities (MedDRA) nomenclature will be used to code adverse events. Adverse events will be coded from the verbatim text into preferred term and system organ class (SOC). The number and percent of patients reporting treatment emergent adverse events will be tabulated based on the primary SOC and preferred terms. Summary tables will be generated for all adverse events regardless of causality as well as treatment-related adverse events for the entire study and by treatment cycle. Other safety variables include vital signs (blood pressure, pulse rate, and temperature) and pregnancy test results. Ocular safety will be evaluated through assessment of visual acuity and visual field, evaluation of macroscopic bulbar conjunctival hyperemia and iris color, assessment of endothelial cell density and corneal thickness, IOP measurement, and biomicroscopic and ophthalmoscopic examinations (including gonioscopy with Bimatoprost SR implant assessment, optic disc examination, and dilated fundus examination).

Ocular adverse events and safety variables will be summarized by Bimatoprost SR or SLT eye, and nonocular safety variables will be summarized by patient. A separate summary will be provided for safety events occurring after nonstudy IOP-lowering medication has been initiated.

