8.4.3.14 Weeks 36, 40, 44, 47, and 52/Exit

The following procedures are performed at Weeks 36 (± 4 days), 40 (± 4 days), 44 (± 4 days), 47 (± 4 days), and 52/Exit (± 7 days):

- Collection of adverse events
- Collection of concomitant medications and procedures
- Vital signs (at rest ≥ 5 minutes)
- Pregnancy test for females of childbearing potential (as defined in [Section 4.5.3](#)) (Week 52/Exit only)

The following procedures should be performed in both eyes (procedures in bold should be done in the order shown):

- **Pre-Hour 0 examinations** (may perform in any order before Hour 0 IOP):
 - Macroscopic conjunctival hyperemia assessment (The examination will also include, [REDACTED])

Approval Date: 27-Mar-2020

- [REDACTED] may be performed at interim visits for appearance of or increase/decrease in hyperemia.)
- Best-corrected visual acuity
 - **Intraocular pressure measurement at Hour 0**
 - **Non-contact examinations:** The following may be performed in any order, at any time before gonioscopy (including prior to Hour 0 IOP):
 - Macroscopic iris color assessment (Week 52/Exit only)
 - Manifest refraction (Week 52/Exit only)
 - Visual field (If dilation is required to perform this test, then the visual field test should be performed after the last IOP measurement of the day.) (Week 52/Exit only)
 - Specular microscopy (Weeks 40 and 52/Exit only)
 - [REDACTED] (at Week 52/Exit at selected sites in both eyes of all consenting patients who underwent assessment at Screening; may be done at interim visits at the discretion of the investigator. Perform any contact assessments following IOP measurements.)
 - Biomicroscopy (The examination will also include, [REDACTED]
[REDACTED]
[REDACTED] may be performed at interim visits for appearance of or increase/decrease in hyperemia.)
 - **Gonioscopy/angle assessment** (The examination will also include, [REDACTED]
[REDACTED].)
 - Pachymetry (Weeks 40 and 52/Exit only) (may be done any time after gonioscopy)
 - **Pupil dilation** (Weeks 40 and 52/Exit only) (post dilation exams below may be performed in any order)
 - Dilated ophthalmoscopy (Weeks 40 and 52/Exit only)
 - Optic disc examination (Weeks 40 and 52/Exit only)
 - Contact interactive response system at Week 52/Exit to report patient's exit status

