**Table 4-6 Schedule of Visits and Procedures: Week 36 through Week 52/Exit**

Visits	Week 36 ±4 days	Week 40 ±4 days	Week 44 ±4 days	Week 47 ±4 days	Week 52/Exit ±7 days
Visit Windows					
Adverse Events	X	X	X	X	X
Concomitant Medications/Procedures	X	X	X	X	X
Vital Signs (at rest ≥ 5 minutes)	X	X	X	X	X
Pregnancy Test					X
Ocular Examinations in bold should be performed in the order shown					
Pre-Hour 0 Exams (may perform in any order before Hour 0 IOP)					
Macroscopic Conjunctival Hyperemia Assessment a	OU	OU	OU	OU	OU
Best-Corrected Visual Acuity b	OU	OU	OU	OU	OU
Intraocular Pressure H0	OU	OU	OU	OU	OU
Non-contact Exams (may perform in any order at any time before gonioscopy)					
Macroscopic Iris Color Assessment					OU
Manifest Refraction b					OU
Visual Field c					OU
Specular Microscopy		OU			OU
XXXXXXXXXX					OU
Biomicroscopy a	OU	OU	OU	OU	OU

Visits	Week 36	Week 40	Week 44	Week 47	Week 52/ Exit
Visit Windows	±4 days	±4 days	±4 days	±4 days	±7 days
Gonioscopy/Angle Assessment	OU e	OU	OU	OU	OU e
Pachymetry (may be done any time after gonioscopy)		OU			OU
Pupil Dilation (perform post-dilation eye exams in any order)		OU			OU
Dilated Ophthalmoscopy		OU			OU
Optic Disc Examination		OU			OU
Contact Interactive Response System f					X

H = Hour; Hour 0 = 08:00 ± 1 hour; IOP = intraocular pressure; OU = both eyes; X = perform procedure

- a [REDACTED] See Procedure Manual for details.
- b Manifest refraction will be used to provide a correction for best-corrected visual acuity testing. At all study visits, if there is a 2-line or more reduction in visual acuity from the last best-corrected visual acuity performed, a repeat manifest refraction in both eyes and best-corrected visual acuity will be performed.
- c For a given patient, the same test methodology must be used for historical fields and all fields performed throughout the study.
- d [REDACTED] Assessment will be performed at Week 52/Exit in patients who underwent assessment at Screening. Perform any contact assessments following completion of IOP measurements. See Procedure Manual for details.
- e [REDACTED] See Procedure Manual for details.
- f Contact at Week 52/Exit to report patient's exit status.

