## 11.0 SAFETY ANALYSES

All safety analyses will be performed using the Safety Population. As indicated in [Section 6.5](#), safety data collected at Screening for eligibility assessment will not be analyzed.

Non-ocular safety assessments include: non-ocular adverse events (AEs), clinical laboratory, vital signs (blood pressure, pulse rate and temperature), and pregnancy test. Ocular safety will be evaluated through: ocular AEs, best corrected visual acuity, visual field examination, specular microscopy, macroscopic iris color assessment, macroscopic conjunctival hyperemia assessment, gonioscopy / angle assessment, biomicroscopy (using a slit lamp), lens assessment, optic disc examination, dilated ophthalmoscopy, pachymetry, and anterior segment-optical coherence tomography.

[REDACTED]

Unless otherwise stated, the last non-missing safety assessment before the SLT treatment (Day 1) will be used as the baseline for all analyses of that safety parameter.

Analysis study periods are defined as follows:

- **During the study:** Date of SLT treatment through Week 52/Exit visit/last study visit available.
- **Analysis Cycle 1:** SLT Treatment date (Day 1) through the second Bim SR implant date – 1. If the second Bim SR implant was not given to a patient, all safety assessments through Week52/Exit visit/last study visit available will be included in analysis cycle1.
- **Analysis Cycle 2:** Second Bim SR implant date through the third Bim SR implant date – 1. If the third Bim SR implant was not given to a patient, all safety assessments through Week52/Exit visit/last study visit available will be included in analysis cycle 2.
- **Analysis Cycle 3:** Third Bim SR implant date through Week 52/Exit visit/last study visit available. Note that only Stage 1 patients were eligible to receive third Bim SR implant.

All summaries will be based on the first treatment received in each eye (Bim SR or SLT), except one patient who received both SLT and Bim SR in the same eye (Safety assessment will be summarized in Bim SR). For non-ocular safety measures, overall summaries will be presented. For ocular safety assessments, summaries will be presented for the periods of during the study, Analysis Cycle 1, Analysis Cycle 2, and Analysis Cycle 3 as shown in Figure 11-1 below.

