## 11.2 VITAL SIGNS

Vital signs (systolic and diastolic blood pressures [mmHg], pulse rate [bpm], and temperature [Celsius]) will be collected at baseline, but will not be analyzed.

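### The SAP leaves vital signs unanalysed, saying they are taken only at Screening, but both documents schedule them at every clinic visit and the protocol lists them as a safety variable

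*SAP*

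**What the plan says.** SAP 6.4 names laboratory tests, vital signs, the pregnancy test, the visual functioning questionnaire and the general physical examination, and says these "are collected only at Screening and will not be analyzed". SAP 11.2 returns to vital signs and says they "will be collected at baseline, but will not be analyzed".

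SAP 11.0 points the other way. Its list of non-ocular safety assessments contains "clinical laboratory, vital signs (blood pressure, pulse rate and temperature), and pregnancy test", and it says overall summaries will be given for non-ocular safety measures. It leaves out only safety data gathered at Screening to judge eligibility, citing a Section 6.5 that the SAP does not contain (presumably 6.4).

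The protocol is consistent on this point. Section 6.3.1.3 says "The below vital signs will be measured at all patient visits". Section 7.3.4, on safety analyses, says "Other safety variables include vital signs (blood pressure, pulse rate, and temperature) and pregnancy test results", and adds that nonocular safety variables are to be summarised by patient.

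**The concern.** The SAP is meant to carry out the protocol's safety analysis. Here its only specific instruction removes a variable that the protocol names, and the statement attached to that instruction is untrue. Leaving eligibility-only data unanalysed would be reasonable. Vital signs are not such data: most of the readings are taken after treatment.

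Two things are at stake. First, the protocol's hypothesis of an acceptable safety profile would be assessed without a summary that the protocol promises. Second, a programmer cannot follow SAP 11.0 together with SAP 6.4 and 11.2, so what is produced would depend on which section is read.

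**Working it through.** No power or error-rate formula applies. The check is a count of scheduled readings, followed by a comparison of the passages.

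**Step 1. Reproduce the protocol's visit count.** Protocol section 8 gives at least 20 visits for a patient who completes all treatments, and 2 more for Stage 1. Counting the clinic visits with a vital-signs mark in the SAP schedules, phone calls excluded:

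| SAP table | Visits with vital signs | Count |
|---|---|---|
| 4-2 | Screening, Baseline, Day 1 | 3 |
| 4-3 | Day 4, Cycle 1 Day 2, Weeks 4, 8, 12, 15 | 6 |
| 4-4 | Week 16, Cycle 2 Day 2, Weeks 20, 24, 28, 31 | 6 |
| 4-6 | Weeks 36, 40, 44, 47, 52/Exit | 5 |
| 4-5 (Stage 1 only) | Week 32, Cycle 3 Day 2 | 2 |

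Two-cycle patient: 3 + 6 + 6 + 5 = 20. Stage 1 patient: 20 + 2 = 22. Both agree with protocol section 8, so vital signs are scheduled at every clinic visit.

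**Step 2. Compare with the SAP 6.4 premise of one visit (Screening).** Patients who did not receive Cycle 2 under Amendment 3 need not attend Week 16 or Cycle 2 Day 2, which gives 20 − 2 = 18.

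| Patient | Visits with vital signs | After Screening (−1) | After Day 1 (−3) |
|---|---|---|---|
| Two cycles | 20 | 19 | 17 |
| Three cycles (Stage 1) | 22 | 21 | 19 |
| Cycle 2 not given (Amendment 3) | 18 | 17 | 15 |

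Protocol 6.3.1.3 has readings taken before any invasive procedure, so the Day 4 reading precedes the first implant. Readings after the first implant are therefore one fewer: 16, 18 and 14.

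**Step 3. Check the rest of the SAP 6.4 sentence against the schedules.**

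- Laboratory samples: Screening only, unless a retest is needed. Correct.
- Physical examination: Screening only. Correct.
- Vital signs: every clinic visit. Wrong.
- Pregnancy test: Baseline and Week 52/Exit. Wrong.
- Visual function questionnaire: Baseline, as SAP 12.0 itself says. Wrong.

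**Step 4. Look for another reason for the omission.** SAP 11.2 gives none, and its timing (baseline) matches neither 6.4 nor the schedules. For laboratory data, SAP 11.3 does give a reason: results are reviewed at the site and any that amount to adverse events are reported as such. Neither document says this about vital signs.

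**The case against.** The strongest reply is that the omission looks deliberate and costs little. SAP 11.2 states the decision in a section of its own without relying on the Screening-only claim, so correcting 6.4 alone would not bring back an analysis. Each patient is planned to receive SLT in one eye and the implant in the other, so systemic readings have no concurrent control and cannot be attributed to either treatment. The safety problem that ended dosing was corneal. A clinically relevant abnormality could still be reported as an adverse event, and SAP 16.4 has all assessments of safety parameters shown in listings. Protocol 7.3.4 promises a summary, but not specifically one by visit or of change from baseline. SAP 17.0, where a change from the protocol would be declared, shows no text in this copy, possibly because it was redacted.

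Much of this stands. The data are not lost, treatment attribution is not possible, and nothing can be concluded from 17.0. It follows that 11.2 must change as well as 6.4. But a deliberate omission still needs a true reason, and none appears in the sections that can be read. Listings and adverse event tables do not show how measured values moved, and they do not replace the patient-level summary in protocol 7.3.4. That commitment does not depend on a between-eye comparison.

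**Conclusion.** The concern holds. SAP 6.4 is factually wrong about when vital signs are collected, SAP 11.2 is wrong in a different way, and both conflict with SAP 11.0 and protocol 7.3.4. Followed as written, 6.4 and 11.2 would leave all 17 scheduled readings after Day 1 unsummarised for a two-cycle patient (19 for Stage 1, 15 where Cycle 2 was not given under Amendment 3).

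These are scheduled counts and assume full attendance. The conclusion also assumes that the separate table specifications and SAP 17.0, neither of which can be read here, do not already resolve the conflict. The consequence is a missing descriptive safety summary and an internally inconsistent SAP. The primary analysis, the ocular safety analyses and adverse event reporting are not affected. It should be corrected.

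**What to change.** 1. Remove vital signs from SAP 6.4. Correct the timing for the pregnancy test (Baseline and Week 52/Exit) and the visual function questionnaire (Baseline).
2. Rewrite SAP 11.2: in the safety population, summarise systolic and diastolic pressure, pulse and temperature by visit, with change from the last pre-SLT value. State whether the Day 1 reading taken before SLT can serve as baseline. The general rule in SAP 11.0 (last value before SLT) appears to allow it, but the baseline window in Table 16-1 ends the day before.
3. Make SAP 11.0 agree with 6.4, 11.2, 11.3 and 11.3.1 on laboratory data, vital signs and pregnancy tests, and correct its reference to Section 6.5.
4. If the sponsor still prefers to omit the summary, state that in SAP 17.0 as a change from protocol 7.3.4, with a reason that fits the actual schedule.

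The cost is SAP wording and one descriptive table. The data are already being collected, and the design and sample size do not change.
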